### 8.2.7 Bath Ankylosing Spondylitis Disease Activity Index (BASDAI)

The BASDAI is a self-administered questionnaire measure used to answer 6 questions (on a Likert scale ranging from 0-10) pertaining the 5 major symptoms of axial activity: 1) fatigue, 2) neck, back or hip pain, 3) joint pain/swelling other than neck, back or hips, 4) areas of localized tenderness, 5) overall level of morning stiffness, and 6) duration of morning stiffness (36). To give each symptom equal

weighting, the mean of the 2 scores relating to morning stiffness is taken. The resulting 0 to 50 score is divided by 5 to give a final 0 to 10 BASDAI score.

#### 8.2.8 Leeds Enthesitis Index (LEI)

The LEI has been developed specifically for use in PsA. It measures enthesitis at 6 sites (lateral epicondyle, left and right, medial femoral condyle, left and right, Achilles tendon insertion, left and right) (37). Each site is assigned a score of 0 (absent) or 1 (present); the results from each site are then added to produce a total score (range 0 to 6). The LEI will be administered by a suitably trained member of the research team.

#### 8.2.9 Leeds Dactylitis Index

If a patient has dactylitis, the LDI-will be administered by site personnel. The LDI has been developed to measure the severity of dactylitis. Once the presence of dactylitis is established in each digit, the ratio of the circumference of the affected digit to the circumference of the digit on the opposite hand or foot is measured (38). Each dactylitic digit is defined by a minimum increase of 10% in circumference over the contra-lateral digit. If the same digits on each hand or foot are thought to be involved, the clinician will refer to a table of normative values for a value which will be used to provide the comparison. The calculated ratio is then multiplied by a tenderness score of 0 (non-tender), 1 (tender), 2 (tender and wince) or 3 (tender and withdraw). Tenderness is assessed in the area between the joints. The results of each digit are then added to produce a total score (39).

#### 8.2.10 Health Assessment Questionnaire-Disability Index

The HAQ-DI is a patient-reported standardized questionnaire that is commonly used in PsA to measure disease-associated disability (assessment of physical function). It consists of 24 questions referring to 8 domains: dressing/grooming, arising, eating, walking, hygiene, reach, grip, and other daily activities(40).

The disability section of the questionnaire scores the patient's self-perception on the degree of difficulty (0 = without any difficulty, 1 = with some difficulty, 2 = with much difficulty, and 3 = unable to do), covering the 8 domains. The reported use of special aids or devices and/or the need for assistance of another person to perform these activities is also assessed. The scores for each of the functional domains will be averaged to calculate the functional disability index.

#### 8.2.11 Minimal Disease Activity (MDA)

Minimal disease activity or MDA (27) is defined as any patient who meets at least 5 of the 7 following criteria:

Tender joint count  $\leq$ 1; Swollen joint count  $\leq$ 1; PASI  $\leq$ 1; Patient pain VAS  $\leq$ 15; Patient global disease activity VAS  $\leq$ 20; HAQ  $\leq$ 0.5; Enthesitis count  $\leq$ 1.

#### 8.2.12 Psoriatic Arthritis Response Criteria (PsARC)

The PsARC (7, 8) is a composite assessment reported in terms of the percentage of patients achieving response according to the following criteria: Physician's Global Assessment of Disease Activity, Patient Global Assessment of Articular Disease Activity, tender joints grading, and swollen joints grading. Overall response is defined by improvement from baseline assessment in 2 of 4 criteria, 1 of which must be a joint count; there must not be worsening in any of the 4 criteria:

1. At least 30% reduction in tender joints grading (grading of 68 joints instructions: as in [appendix 7](#); CMC and DIP of the feet excluded)

2. At least 30% reduction in swollen joints grading (grading of 66 joints instructions: as in [appendix 7](#); CMC, hips and DIP of the feet excluded)
3. At least a 1 point reduction in physician's assessment of articular disease (1-5 Likaert scale)
4. At least a 1 point reduction in patient's assessment of articular disease (1-5 Likaert scale)

## 8.2.13 American College of Rheumatology 20 Responder Index (ACR20)

ACR20 response (6) is an efficacy measure for which a patient must have:

- ≥20% improvement in both TJC (68 joints count: as in [appendix 7](#); CMC and DIP of the feet excluded) and SJC (66 joints count: as in [appendix 7](#); CMC, hips and DIP of the feet excluded) and
- ≥20% improvement in at least 3 of the following 5 ACR Core set criteria:
  1. Patient's Assessment of Pain on Visual Analogue Scale (VAS)
  2. Patient's Global Assessment of Articular Disease Activity VAS
  3. Physician's Global Assessment of Disease Activity VAS
  4. Patient's Assessment of Physical Function as measured by the HAQ-DI
  5. Acute phase reactant as measured by CRP

## ACR50 and ACR70

ACR50 and ACR70 responses are secondary efficacy endpoints and are improvements of at least 50% and of at least 70%, respectively, in the multiple disease assessment ACR criteria. The ACR50 and ACR70 are calculated similarly to ACR20, as described above.

## 8.2.14 Composite Psoriatic Disease Activity Index

Composite Psoriatic Disease Activity Index is a validated instrument intended to assess composite psoriatic disease activity and response to therapy (30). This instrument assesses individual domains involved as well as the global effect of disease in all dimensions by which each patient may be affected. Domains include peripheral arthritis as assessed by the number of tender (68 joints count: as in [appendix 7](#); CMC and DIP of the feet excluded) and swollen (66 joints count: as in [appendix 7](#); CMC, hips and DIP of the feet excluded) joint and the Health Assessment Questionnaire (HAQ), skin as assessed by the PASI and the DLQI, enthesitis as assessed by the number of sites with enthesitis and the HAQ, dactylitis as assessed by the number of digits affected, and spinal disease as assessed by the BASDAI and ASQoL (41). Scores range from 0 to 15 for assessment including spinal disease (BASDAI and ASQoL) and 0 to 12 for assessment excluding spinal disease, with a higher score indicating higher disease activity.

## 8.2.15 Measures of skin disease activity

### 8.2.15.1 Percentage of Body Surface Area (BSA)

The investigator will evaluate the percentage involvement of skin psoriasis (Pso) on each patient's BSA on a continuous scale from 0% = no involvement to 100% = full involvement, where 1% corresponds to the size of the patient's handprint including the palm, fingers, and thumb.

### 8.2.15.2 Psoriasis Area and Severity Index (PASI 75, PASI 90, PASI 100)

If the patient has skin affected by plaque Pso, the PASI will be administered by site personnel. The PASI combines assessments of the extent of body-surface involvement in 4 anatomical regions (head, trunk, arms, and legs) and the severity of desquamation, erythema, and plaque induration/infiltration (thickness) in each region, yielding an overall score of 0 for no Pso to 72 for the most severe disease

(28). Patients achieving PASI 75, 90, or 100 are defined as having an improvement of at least 75%, 90%, or 100%, respectively, in the PASI compared to baseline.

#### **8.2.15.3 Modified Nail Psoriasis Severity Index (mNAPSI)**

A modification to the NAPSI (the modified Nail Psoriasis Severity Index, mNAPSI) removed the division of the nail into quadrants and scores pitting and crumbling on a scale from 0-3. Oil drop discolouration and onycholysis were also combined, as it was felt they represent the same pathology. In the newly modified method, each fingernail is scored for the presence and the severity of pitting, onycholysis/oil-drop dyschromia and nail plate crumbling (score 0-3) and the presence or absence of splinter haemorrhages, leuconychia, red spots in the lunula and nail bed hyperkeratosis (score 1 for each if present). We are planning to assess the oil drop dyschromia or discolouration as an independent feature (0-1) (see [appendix 4](#)). This gives a total possible score of 140. Validation as part of the original study found excellent inter-rater reliability, along with good correlation with a physician nail VAS and good intra-rater reliability (29).

### **8.2.16 Quality of life and health status measures**

#### **8.2.16.1 SF-36**

The SF-36 is a multi-purpose, short-form health survey with 36 questions (32). It yields an 8-scale profile of functional health and well-being scores as well as psychometrically-based physical and mental health summary measures and a preference-based health utility index. It is a generic measure, as opposed to one that targets a specific age, disease, or treatment group.

#### **8.2.16.2 Dermatology Life Quality Index**

The DLQI is a simple, patient administered, 10 question, validated, quality of life questionnaire that covers 6 domains including symptoms and feelings, daily activities, leisure, work and school, personal relationships and treatment. Response categories include “not at all”, “a lot” and “very much” with corresponding scores of 1, 2 and 3 respectively and unanswered (“not relevant”) responses scored as “0”. Totals range from 0 to 30 (less to more impairment) and a 5-point change from baseline is considered clinically relevant (31).

## **8.3 Assessment of other efficacy variables**

### **8.3.1 Ultrasound of joints and entheses**

Ultrasound (US) of hands and feet and lower and upper limb joints and entheses (Achilles, plantar fascia insertion, quadriceps insertion, patellar tendon origins and insertions and common extensor tendon origins of the elbow) will be performed at week 0, 12, 24 and 36 within ten days before or after the scheduled visit attendance using a multiplanar technique with symmetrical scanning. All scans will be performed, whenever possible, by the same ultrasonographer with specialist training in scanning entheses. The room will be maximally darkened starting from the beginning of the ultrasound assessment. Joints and enthesal sites will be assessed for the presence of grey scale (GS) abnormalities and power Doppler (PD) signal.

Pre-defined joints will be scanned for the presence of synovitis and bone erosions as per established rheumatoid arthritis (RA) protocols as there is currently no validated system for PsA. Synovitis will be scored according to the EULAR-OMERACT definitions for RA (42, 43) for gray scale, power Doppler and a combined PDUS score for each joint (0 if GS=0, otherwise highest of either gray scale or power Doppler score); the total of these individual PDUS scores is the Global OMERACT-EULAR Score System (GLOESS). US enthesopathy will be identified according to OMERACT definitions (44, 45). Enthesopathy is defined as ‘abnormally hypoechoic (loss of fibrillar architecture) and/or thickened

tendon or ligament at its bony attachment (may occasionally contain hyperechoic foci consistent with calcification), seen in two perpendicular planes, which may exhibit Doppler signal and/or bony changes including enthesopathy, erosions or irregularity.'

Entheseal thickening will be evaluated relative to the body of the tendon. When PD signal is detected at the cortical bone insertion, it will be considered enttheseal. When PD signal is detected at the tendon body and/or adjacent bursitis, it will be considered perienttheseal and therefore not documented.

Thickness and erosion assessments will be scored quantitatively. Thickness findings will be scored on a scale between 0 and 3.

Grade 0: <1mm exceeding the normal threshold

Grade 1:  $\geq 1\text{mm}$  but  $< 2\text{mm}$  exceeding the normal threshold

Grade 2:  $\geq 2\text{mm}$  but  $< 3\text{mm}$  exceeding the normal threshold

Grade 3:  $\geq 3\text{mm}$  exceeding the normal threshold

The maximum diameter of erosions will also be scored quantitatively:

Grade 1:  $>0$  but  $<2\text{mm}$

Grade 2:  $\geq 2$  but  $<3\text{mm}$

Grade 3:  $\geq 3\text{mm}$

Entheseal power Doppler will be scored on a semi-quantitative basis:

Grade 1: Mild changes

Grade 2: Moderate changes

Grade 3: Severe changes

The remainder of the assessments (hypoechoicity, enthesophytes, calcifications) will be scored present (1) or absent (0).

Once all aspects have been scored, the cumulative totals will be calculated to formulate and 'inflammation score' and a 'chronicity score'

Inflammation score: GS changes related to inflammation (enttheseal hypoechoicity and thickening) will be added to the PD scores.

Chronicity score: GS changes related to chronic findings (calcifications, erosions and enthesophytes) will be totalled.

US scores forming secondary endpoints will include 24 joints (bilateral wrists, MCPs 2&3, PIPs 2&3, knees, MTPs 1-5, ankle) and 10 entheses (bilateral quadriceps insertion, patellar ligament proximal insertion, patellar ligament distal insertion, Achilles tendon, plantar fascia). Exploratory analysis of synovitis and enthesitis will be performed in a subset of patients using scores calculated according to the newly published OMERACT definitions which include 48 joints (bilateral wrists, MCP1-5, PIP1-5, DIP2-5, knees, MTP1-5, tibiotalar, talonavicular and subtalar) and 12 entheses (bilateral lateral

epicondyle, quadriceps insertion, patellar ligament proximal insertion, patellar ligament distal insertion, Achilles tendon, plantar fascia) (42, 43).

Patients will be considered to be in US remission if the maximum score for any of the joints forming part of the established RA scoring protocol, and for any of the entheses scanned in all patients, is GS enthesal hypoechoogenicity score <2 and power Doppler score=0. On an exploratory basis this will be repeated using scores calculated in the joints and entheses included in the OMERACT definitions, in the subset of patients with these scores available.

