All subjects reaching 24 weeks (primary endpoint) will be invited for repeat WB-MRI (if in WB-MRI subset) and US examination of a set core of joints and entheses (as per baseline assessment). Subjects will also be assessed for PASDAS (primary outcome), MDA and PsARC and other relevant clinical outcomes.

Subjects in Treatment arm 1 (GOL+MTX) will have GOL discontinued at week 24, will continue MTX and will be observed thereafter for the duration of the observational phase of the study (until week 52). In case of disease flare during this period (defined as in [section 8.18](#)), subjects will be invited to have repeated imaging assessments (US and WB-MRI as per “Extra visit” [section 8.6](#)) and will be treated according to existing clinical protocols and NICE guidelines. Observation will not be interrupted and all data from these participants will be collected until the end of the study period.

Subjects in Treatment arm 1 not achieving PsARC improvement by week 24 will have GOL discontinued and will be treated according to existing clinical protocols and NICE guidelines, and will be observed until the end of the study period.

Subjects on Treatment arm 2 (MTX+placebo) achieving PsARC improvement at week 24 will be allowed to continue their MTX treatment and shall be observed for the duration of the observational phase of the study (until week 52). In case of disease flare (defined as in [section 8.18](#)) beyond week 24, subjects will be invited to have repeated imaging assessments (WB-MRI if in WB-MRI subset), US as per "Extra visit" and will be treated according to existing clinical protocols and NICE guidance.

Subjects on Treatment arm 2 not achieving PsARC improvement by week 24 will be treated according to existing clinical protocols and NICE guidance and observed until the end of the study Period.

**Corticosteroids:** Patients on both groups can receive further IM/IA corticosteroids at weeks 8 and 12 if a PsARC response is not achieved at these visits. The maximum amount of corticosteroids given between these 2 visits should not exceed 120mg intramuscular methylprednisolone (or comparable amount intra-articularly; unless contraindicated or not tolerated). No further corticosteroids are allowed between weeks 12 and 24.

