#### **2. Corticosteroids**

Period 1 (Double blind randomised phase): Both groups will receive corticosteroids at baseline up to a dose of 120 mg methylprednisolone (unless contraindicated or not tolerated). This will be performed

either as a stat bolus intra-muscular injection (if  $\geq 4$  swollen joints) or as intra-articular injections (to a maximum of 4 joints injected per visit; 20-80mg per joint with the remainder, if appropriate, given as an intra-muscular injection). In addition, any swollen joint observed at subsequent visits (only at either week 8 or at week 12) may be injected with methylprednisolone (20-80 mg per joint) to a maximum dose of 120 mg methylprednisolone into a maximum of four joints between both visits. In case of  $\geq 4$  swollen joints at either week 8 or at week 12, a dose of methylprednisolone 120 mg IM could be administered instead of intra-articular injections. Any injections at baseline will ONLY be done after the baseline US and WB-MRI scan has been performed. No corticosteroid injections will be allowed between weeks 12 and 24. Other limitations apply as outlined in [section 7.3](#).

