**4.** WB-MRI (if required) should be performed within ten days before or after the scheduled follow-up visit attendance. To comply with MRI guidance, the blood test urea & electrolytes (U&Es) needs to be up-to-date (within 4 weeks of each scan). Baseline scans should always be performed before randomization.

**IMPORTANT:** WB-MRI data is being used to support an exploratory endpoint, from a subset of randomised participants; WB-MRI scans will not be performed in any patients once the required sample size has been reached.

**5.** US should be performed within ten days before or after the scheduled follow-up visit attendance.

**6, 7.** No imaging (WB-MRI and/or US) to be performed if: a) withdrawal visit (numbered 99) occurs within 6 weeks of last imaging; b) flare visit (numbered 98) occurs after week 36; or if within 6 weeks of last imaging.

**8.** IMP administration should be every four weeks. In the case of a missed dose of IMP, the IMP can be administered at the next scheduled visit. Exposure to IMP should be captured in the medication workbook. All timed visits should take place within a seven-day window of the ideal target visit date (with the exception of the screening and baseline visits).

\* Week 44: Participants will be re-supplied with anti-rheumatic drugs at this time-point, as part of NHS standard of care. The study physician will prescribe the relevant drug(s) according to local procedures. Laboratory tests will be performed according to the prescription-related monitoring requirements. No trial-related data will be collected at this time-point.

\*\*Study week X: withdrawal visit. Subjects who discontinue prematurely during Period 1 should return for assessments associated with Week 24 visit. Participants who withdraw their consent at either period 1 or 2 should return for assessments associated with Week 24 visit (exceptions apply as per points 6,7 of this legend). See also [section 6.5](#)

\*\*\* Study week Y: extra visit to be performed only in case of flare of psoriatic arthritis. It applies only to period 2 (observational, after week 24 until week 52). For definition and management of flare between week 0 and week 24, refer to [section 8.18](#)

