## 8.11 Week 12, $\pm 7$ days (secondary endpoint)

- Confirmation of on-going consent
- Adverse events evaluation.
- Concomitant medication.
- Duration of articular morning stiffness.
- PsA-related comorbidities.
- Vital signs (blood pressure after a 5-minute rest, pulse rate and body temperature).
- Measurement of body weight.
- Blood tests:
  - Haematology, blood chemistry.
  - CRP and ESR.
- Compliance assessment.
- Response Assessment - Joint examination with swollen and tender joint counts/grading and patient and physician assessments of articular disease on Likaert scale for PsARC assessment.
- US scan (performed as per footnote following summary schedule, [section 8.6](#)).
- Enthesitis, dactylitis, nail and skin assessments
- Physician VAS
- Patient-reported outcomes (disease activity and pain VAS, HAQ, SF-36, DLQI, ASQoL, BASDAI)
- Sample collection for biological sub-study.
- Dispense study drugs according to treatment arm.
- Administer 120 mg intramuscular methylprednisolone if  $\geq 4$  joints involved (unless contraindicated or not tolerated) or consider intra-articular steroid injections (as per an equivalent dose of methylprednisolone – see [section 7.6.2](#)) if PsARC response not achieved.

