11.3 Other Efficacy Variable Analyses

A number of sensitivity analyses will be conducted. In addition to sensitivity analyses relating to missing data or outliers (see section 8.2) and stratification status (see section 11.1), a per protocol analysis will be performed, repeating the primary endpoint analysis in the Per Protocol Set. In addition, comparisons will be made between PsARC response status calculated using the 68/66 tender/swollen counts originally specified by the criteria and response status calculated using the extended 78/76 joint counts. McNemar's tests will be used to compare response status according to the reduced and expanded joint counts. This will be performed in the observed data (i.e. without imputation).

See section 8.6 for details of planned exploratory analysis of baseline predictors of response to treatment.

In a subset of patients, total synovitis and enthesitis scores calculated in expanded sets of joints defined in the newly published OMERACT definitions will be compared between groups according to the same methods as for secondary outcomes. This will be conducted in the subset of participants with for whom the expanded joint scores were collected at screening. In addition, for patients in the WB-MRI subset the WB-MRI lesion scores will be compared between groups on an exploratory basis using the same methods as for secondary outcomes. However, the focus will be on quantifying the potential treatment effect. A range of confidence intervals (75%, 85%, 95%) around the difference between the treatment arms will be calculated, to indicate the level of confidence with which we could say there was potential for a substantive difference between groups. The biomarker sub-study data (available in a subset of patients) are to be analysed separately as part of a number of collaborative projects with other centres. Analysis plans for these projects will be produced separately.

An assessment of the test-retest reliability of the PASDAS will be performed, by calculating the intraclass correlation coefficient ($ICC_{(1,1)}$) between PASDAS measurements collected at screening and baseline; a 95% confidence interval will be constructed.

If sufficient patients in each group receive additional steroid injections at week 8, g-methods will be used to investigate the extent to which this is associated with total PDUS (US GLOESS) score at week 12.

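### Nothing requires the week-12 ultrasound to precede the week-12 steroid injection, so the week-12 ultrasound endpoints and the planned steroid analysis could be distorted, in a direction and by an amount the documents cannot fix

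*Protocol*

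**What the plan says.** **Scan window.** Protocol 8.3.1 says ultrasound "will be performed at week 0, 12, 24 and 36 within ten days before or after the scheduled visit attendance". Footnote 5 to the schedule in 8.6 repeats the window: "US should be performed within ten days before or after the scheduled follow-up visit attendance". Neither mentions steroid.

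**Steroid at week 12.** Protocol 5.1: "Patients on both groups can receive further IM/IA corticosteroids at weeks 8 and 12 if a PsARC response is not achieved at these visits". The week-12 visit list (8.11) provides for an intramuscular dose, or to "consider intra-articular steroid injections (as per an equivalent dose of methylprednisolone", under the condition "if PsARC response not achieved". One sentence in 7.6.2 carries no PsARC condition: "any swollen joint observed at subsequent visits (only at either week 8 or at week 12) may be injected with methylprednisolone". These passages must be reconciled.

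**Cap.** Protocol 5.1 limits steroid at weeks 8 and 12 combined to 120 mg methylprednisolone per patient. SAP 3.2.2 records from blinded data that everyone given additional steroid had a single 120 mg intramuscular dose.

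**Order rules elsewhere.** For baseline, 7.6.2 states: "Any injections at baseline will ONLY be done after the baseline US and WB-MRI scan has been performed". At week 24, steroid is released only once that visit's trial procedures are complete (7.3, 7.6.2). Thereafter injections are barred if a clinical or imaging assessment is due within six weeks (5.1, 7.6.2).

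**Analysis.** Week-12 ultrasound scores and ultrasound remission are secondary endpoints (Protocol 3.2, SAP 3.2.2). SAP 8.6 does not adjust for steroid received. If enough patients are injected at week 8, SAP 11.3 says "g-methods will be used to investigate the extent to which this is associated with total PDUS (US GLOESS) score at week 12".

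**The concern.** At week 12 the joint assessments that decide whether a patient is injected are made before the injection, while the ultrasound of the same visit may be made before or after it. If steroid lowers ultrasound scores within days, a late scan records the disease state plus the response to a new dose, and whether it does so depends on booking. The injection goes to patients who are doing badly. If those are more often in the control arm, late scans would lower control scores more and shrink the arm difference in week-12 GLOESS, enthesitis inflammation score and ultrasound remission.

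The second use of the same scans is the week-8 steroid analysis, which serves a stated secondary objective: whether ultrasound responses are associated with steroid therapy. Late scans would add an unrecorded second exposure to it.

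**Working it through.** **1. The plan's own figure.** The documents give no sample size or power for ultrasound. The PASDAS calculation reproduces: n per arm = 2 × (1.960 + 0.842)² × 1.57² / 1² = 38.7, so 39, or 78 in total. Then 39/0.95 rounds up to 42 per arm (84) and 39/0.90 to 44 per arm (88).

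**2. Order of steroid and scan at each ultrasound time point.**

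| Time | Steroid | Order rule |
|---|---|---|
| Baseline | Bolus, both arms | Imaging first (7.6.2) |
| Week 12 | If no PsARC response | None |
| Week 24 | Permitted | After week-24 procedures (7.3, 7.6.2) |
| Week 36 | Permitted | Not if an assessment is due within 6 weeks (5.1, 7.6.2) |

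The SAP does not close the gap. Its ±14-day rule (8.2) refers to visits and would keep a scan done 10 days after an on-time visit. The missing-data sensitivity analyses (8.2) do not look at scan order.

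**3. Shift in the week-12 arm difference.** Shift = d × q × e, where
- d = proportion injected at week 12, control minus golimumab;
- q = share of injected patients scanned afterwards;
- e = steroid effect on the score at the scan, in SD.

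None of these is in the documents. For scale I assume a true ultrasound effect of 1/1.57 = 0.637 SD, borrowed from the primary endpoint, and 40 per arm (84 × 0.95 / 2 ≈ 40). Power is then 81% (normal approximation).

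| d | q | e | Shift (SD) | Share of 0.637 | Power |
|---|---|---|---|---|---|
| 0 | any | any | 0 | 0% | 81% |
| 0.10 | 0.5 | 0.3 | 0.015 | 2% | 79% |
| 0.20 | 0.5 | 0.8 | 0.080 | 13% | 70% |
| 0.40 | 1 | 0.8 | 0.320 | 50% | 29% |

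**4. What the shared cap does to d.** A patient given the full dose at week 8 cannot be injected at week 12. Let N be week-8 non-response, u the share of those dosed in full at week 8, a the week-12 non-response among undosed week-8 non-responders, and b that among week-8 responders. If all who are eligible at week 12 are injected:

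proportion injected at week 12 = N(1 − u)a + (1 − N)b.

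Three assumed sets, control/golimumab:
- N 0.50/0.25, a 0.7/0.5, b 0.15/0.10
- N 0.60/0.30, a 0.7/0.5, b 0.15/0.10
- N 0.40/0.20, a 0.6/0.4, b 0.10/0.10

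First set, u = 0: control 0.50 × 0.7 + 0.50 × 0.15 = 0.425; golimumab 0.25 × 0.5 + 0.75 × 0.10 = 0.200; d = 0.225. First set, u = 1: control 0.50 × 0.15 = 0.075; golimumab 0.75 × 0.10 = 0.075; d = 0.

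| u | d across the three sets |
|---|---|
| 0 | +0.14 to +0.26 |
| 0.5 | +0.06 to +0.125 |
| 0.8 | +0.012 to +0.045 |
| 1 | −0.02 to 0 |

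The d = 0.40 row in step 3 lies outside this range. With d = 0.26 and e = 0.8, the shift is 0.26 × 0.5 × 0.8 = 0.104 SD (16% of 0.637) if half are scanned late, and 0.208 SD (33%) if all are. With d = −0.02, q = 1 and e = 0.8 it is −0.016 SD, about 2.5% away from no difference.

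**5. The week-8 steroid analysis.** Given the cap and the single 120 mg dose per recipient, nobody injected at week 12 was injected at week 8. All post-injection scans therefore fall among the comparators. On the assumed a of 0.4 to 0.7 and q = 0.5, the mean for undosed week-8 non-responders drops by between 0.4 × 0.5 × e = 0.20e and 0.7 × 0.5 × e = 0.35e. If steroid lowers GLOESS, that pulls the estimated week-8 effect towards zero.

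**6. Does dropping late scans cure it?** Assume 30% of control and 10% of golimumab injected, half scanned late, and non-responders scoring D higher than the rest. After exclusion the non-responder share falls in control from 0.30 to 0.15/0.85 = 0.176 (by 0.124) and in golimumab from 0.10 to 0.05/0.95 = 0.053 (by 0.047). The arm difference shrinks by about 0.076D. The bias removed is (0.30 − 0.10) × 0.5 × e = 0.10e. Exclusion does more harm than good once D exceeds 0.10e/0.076, about 1.3e.

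**The case against.** A reader might infer that the gap biases the week-12 ultrasound comparison towards no difference. The documents do not support that as a fact. The quantity that matters is the arm difference in week-12 injections, not in non-response. Week-8 dosing uses up non-responders first, and more of them in the arm doing worse, so the week-12 difference may be near zero or slightly reversed. This objection stands.

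A size in GLOESS points is equally unsupported. No response rates by arm, scan-to-injection intervals or steroid effects are given, and SAP 11.4 speaks of a lack of substantive change in GLOESS, which lends no support to a large short-term fall.

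It can also be said that steroid is part of the strategy in both arms, so its effect belongs in the comparison. That does not answer the point: the week-12 dose then counts for some injected patients and not others, according to scan date.

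On the steroid analysis, it is correct that no week-8 recipient is doubly exposed and that the analysis runs only if numbers allow. The exposure of its comparators remains. Finally, only one time point of one secondary family is involved, and SAP 11.2 makes all secondaries exploratory if the primary is not significant. That bears on severity and stands.

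**Conclusion.** The gap is real, out of line with the protocol's own handling of imaging at other visits, and not covered by the SAP. It could distort the week-12 ultrasound secondary endpoints. Dilution is plausible if golimumab works and week-8 dosing was incomplete, but neither sign nor size can be fixed. Under the assumptions shown, the shift runs from slightly away from no difference, through zero, to about a sixth of the assumed effect with half the scans late, or a third with all of them late. Every input to that range is an assumption, including the true effect borrowed from PASDAS.

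The clearer direction is in the week-8 steroid analysis, where late scans can only contaminate the comparators. That still requires late scans to exist and steroid to lower GLOESS.

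PASDAS at week 24 and the week-24 ultrasound do not depend on when the week-12 scan was taken. Severity: minor.

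**What to change.** **Protocol 8.3.1 and footnote 5 of 8.6:** require the week-12 scan within the 10 days before the visit, or on the visit day before any injection. This moves the scan and leaves the steroid rules alone. The cost is tighter booking. Since enrolment was planned to end in February 2022, it may serve only as a lesson for a later trial. Separately, reconcile 5.1 and 8.11 with the sentence in 7.6.2 that has no PsARC condition.

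**SAP 11.2 and 11.3:** report the week-12 scan date relative to any week-12 injection, by arm. Repeat the week-12 ultrasound analyses and the week-8 steroid analysis without post-injection scans, as a sensitivity analysis only. SAP 4.0 already postdates unblinding, so label this post hoc if it is added now. State that the exclusion is itself post-randomisation and selectively removes non-responders.

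Do not set these scans to missing in the main analysis. Step 6 shows that removal can shrink the arm difference by more than the bias it cures, and the imputation predictors named in SAP 8.2 do not include week-12 PsARC status or injection. The cost is one table and two repeat analyses, using dates the trial should already hold. If few scans followed an injection, the table alone closes the matter.
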